### Causality assessment:

The relationship of an adverse event to the administration of the study drug is to be assessed according to the following definitions:

No (unrelated, not related, unlikely to be related) – The time course between the administration of study drug and the occurrence or worsening of the adverse event rules out a causal relationship and another cause (concomitant drugs, therapies, complications, etc.) is suspected.

Yes (possibly, probably, or definitely related) – The time course between the administration of study drug and the occurrence or worsening of the adverse event is consistent with a causal

relationship and no other cause (concomitant drugs, therapies, complications, etc.) can be identified.

The definition implies a reasonable possibility of a causal relationship between the event and the study drug. This means that there are facts (evidence) or arguments to suggest a causal relationship.

The following factors should also be considered:

- The temporal sequence from study drug administration-
  - The event should occur after the study drug is given. The length of time from study drug exposure to event should be evaluated in the clinical context of the event.
- Underlying, concomitant, intercurrent diseases-
  - Each report should be evaluated in the context of the natural history and course of the disease being treated and any other disease the subject may have.
- Concomitant drug-
  - The other drugs the subject is taking or the treatment the subject receives should be examined to determine whether any of them might be recognized to cause the event in question.
- Known response pattern for this class of study drug-
  - Clinical and/or preclinical data may indicate whether a particular response is likely to be a class effect.
- Exposure to physical and/or mental stresses-
  - The exposure to stress might induce adverse changes in the recipient and provide a logical and better explanation for the event.
- The pharmacology and PK of the study drug-
  - The known pharmacologic properties (absorption, distribution, metabolism, and excretion) of the study drug should be considered.

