#### **3.3.1 Criteria for Temporary Suspension of Dosing**

Dosing within a cohort or between cohorts will be temporarily suspended until a full cumulative data review is complete if any of the following occur:

- Any study drug-related SAE grade 3 or higher based on Common Terminology Criteria for Adverse Events (CTCAE) Version 5.0
- Any single subject whose ECG (average triplicate ECGs as interpreted by central read) demonstrates a heart-rate corrected QTcF interval (QTcF) >500 msec or in whom there is an increase in QTcF >60 msec from baseline (confirmed by repeat ECG)
- Any new ECG abnormality deemed clinically significant by the investigator
- Any study drug-related cardiac adverse event. In the event that a subject experiences a vasovagal or near-syncopal episode, dosing within a cohort or subsequent cohort may proceed as planned unless the episode is associated with ECG abnormality or the event is deemed to be severe in intensity (severity) by the Investigator
- A study drug-related adverse event from a single System Organ Class deemed to be of moderate intensity (severity) in 4 or more subjects

- Any of the following laboratory abnormalities that are thought to be study drug-related or in which an alternative explanation is not reasonable:
  - ALT or AST  $>8 \times$  the upper limit of normal (ULN), or
  - ALT or AST  $>5 \times$  ULN and persist for more than 2 weeks, or
  - ALT or AST  $>3 \times$  ULN in conjunction with elevated total bilirubin  $>2 \times$  ULN or international normalized ratio  $>1.5$ , or
  - ALT or AST  $>3 \times$  ULN with appearance of fatigue, nausea, vomiting, right upper quadrant pain or tenderness, fever, rash, and/or eosinophilia ( $>5\%$ )
- Any single subject who develops serious study drug-related electrolyte abnormalities due to vomiting and/or inability to maintain adequate oral hydration that impacts cardiac stability
- Other conditions as deemed medically appropriate based on the Investigator's judgement

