### 8.1.1 Adverse (Drug) Reaction

All noxious and unintended responses to a medicinal product related to any dose should be considered an adverse drug reaction. “Responses” to a medicinal product means that a causal relationship between a medicinal product and an adverse event is at least a reasonable possibility, ie, the relationship cannot be ruled out.

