### 8.1.3 Assessment of Adverse Events by the Investigator

The Investigator will assess the severity (intensity) of all adverse events (serious and non-serious) and will be graded using the CTCAE Version 5.0 criteria as shown in Table 1. The Investigator will also categorize each adverse event as to its potential relationship to study drug using the categories of yes or no.

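### The Yes and No causality definitions in Protocol 8.1.3 leave out events with plausible timing and another identifiable cause, and conflict with 8.1.1, so relatedness can be coded inconsistently

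*Protocol*

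**What the plan says.** Protocol 8.1.3 asks the investigator to "categorize each adverse event as to its potential relationship to study drug using the categories of yes or no". There is no third option.

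The causality text in the same section then defines the two answers.

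- The negative answer is labelled "No (unrelated, not related, unlikely to be related". Its text requires that the time course "rules out a causal relationship and another cause (concomitant drugs, therapies, complications, etc.) is suspected".
- The positive answer is labelled "Yes (possibly, probably, or definitely related". Its text requires timing consistent with a causal "relationship and no other cause (concomitant drugs, therapies, complications, etc.) can be identified".

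A sentence after the *Yes* definition says that it implies a reasonable possibility of causation. A list of factors to consider follows, including underlying disease, concomitant drugs and class effects.

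Protocol 8.1.1 defines an adverse drug reaction more broadly: a causal relationship "is at least a reasonable possibility, ie, the relationship cannot be ruled out". It does not require other causes to be absent.

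Relatedness then feeds mandatory rules. The first suspension criterion in Protocol 3.3.1, for example, is "Any study drug-related SAE grade 3 or higher based on Common Terminology Criteria for Adverse Events (CTCAE) Version 5.0". SAP 2.2.3.1 and 2.2.3.2 repeat the suspension and cessation criteria, and SAP 3.9.1 tabulates drug-related events. The SAP gives no definition of relatedness of its own.

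**The concern.** Both definitions join two conditions with *and*, and neither is the complement of the other. An event that starts at a plausible time after dosing, in a subject who also has another identifiable cause, fails *Yes* because of the other cause. It fails *No* because the timing does not exclude the drug. The form still forces one of the two answers.

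This middle case is easy to picture in this trial. Protocol 4.3 requires current upper gastrointestinal symptoms at randomization. Protocol 1.4 notes that post-marketing QT reports with oral domperidone included patients with confounding risk factors, electrolyte disturbance or concomitant treatment. The electrolyte criterion in 3.3.1 concerns abnormalities arising from vomiting or poor hydration, and vomiting is also a symptom of the disease.

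At stake is the consistency of a variable that mandatory suspension and cessation rules and the safety tables take as input. If one site follows the label and another the operative text, the same clinical event counts at one and not at the other.

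**Working it through.** The documents state no figure on this point, so there is nothing to reproduce. The check sets the definitions side by side, counts where relatedness is used, and adds one illustration.

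**Step 1. Exhaustiveness.** There are two factors: whether timing is consistent with the drug or rules it out, and whether another cause is present.

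| Timing | Other cause | *Yes* text met | *No* text met | Assigned | Reaction under 8.1.1 |
|---|---|---|---|---|---|
| Consistent | Absent | yes | no | *Yes* | yes |
| Consistent | Present | no | no | neither | yes |
| Rules out | Absent | no | no | neither | no |
| Rules out | Present | no | yes | *No* | no |

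Two of the four cells are unassigned. The second row matters for safety: 8.1.1 would count the event (taking consistent timing to mean that the relationship cannot be excluded), but the *Yes* text does not. The third row has less safety consequence.

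**Step 2. Labels against text.** The *Yes* label includes events possibly related, while its text bars any event with another identifiable cause. The *No* label includes events unlikely to be related, while its text demands timing that excludes causation. Each label is wider than its own definition.

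**Step 3. Where relatedness is used.**

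- Protocol 3.3.1 has eight criteria. Four depend solely on relatedness: SAE of grade 3 or higher, cardiac event, moderate events in one System Organ Class in four or more subjects, and electrolyte abnormality. The laboratory criterion depends on it in part, because it also applies where no alternative explanation is reasonable. The other three (QTcF, new ECG abnormality, investigator judgement) do not use it.
- Protocol 3.3.2 has two criteria. The SAE criterion uses relatedness and the QTcF criterion does not.
- SAP 3.9.1 has eight overview rows. Three use relatedness: related TEAEs, related serious TEAEs, and related TEAEs leading to discontinuation.
- SAP 3.4.3 also excludes subjects with a related serious or severe event from the Per-Protocol Population.

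**Step 4. Illustration of sensitivity to the reading.** Let p be the true proportion of subjects with a moderate event in one System Organ Class that 8.1.1 would count, and q the share of those events recorded as *Yes*. Both are assumptions. Take n = 15, the subjects on CIN-102 in one cohort (Protocol 3.1), and ignore placebo. The chance of reaching four subjects is P(X ≥ 4) with X ~ Binomial(15, pq).

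| p | q = 1 | q = 0.75 | q = 0.5 |
|---|---|---|---|
| 0.1 | 0.056 | 0.022 | 0.005 |
| 0.2 | 0.352 | 0.177 | 0.056 |
| 0.3 | 0.703 | 0.446 | 0.177 |

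For a criterion met by one related event, 1 − (1 − pq)^15 at p = 0.05 gives 0.537 with q = 1 and 0.316 with q = 0.5.

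The fall as q decreases is built into the set-up, since q cannot exceed 1. The tables show that the rules are sensitive to how the middle case is coded. They do not estimate what will happen.

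**The case against.** The strongest reply is that the text as a whole steers the assessor. The two labels together look complete, an investigator who thinks an event possibly related has a box for it, and the reasonable-possibility sentence restates the 8.1.1 standard. The factor list asks for weighing, which would be pointless if any identifiable alternative barred *Yes*. This has force: many investigators may well record the middle case as *Yes*. It does not remove the conflict, because the relationship is to be assessed by the definitions, and the *Yes* definition still carries the condition that no other cause be found.

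A reader might infer more: that related events will be under-counted, that triggers will fail to fire, and that expedited reporting will suffer. The documents do not support this.

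- **Direction.** The middle case fails *No* as well as *Yes*, and the *Yes* label favours inclusion. Nothing says which way investigators will default.
- **Frequency.** It is not shown that another cause is nearly always present. Under Protocol 8.1, conditions present at first dose are medical history unless they change in severity, frequency or seriousness.
- **Expedited reporting.** Protocol 8.5 concerns suspected unexpected serious reactions and does not refer to the yes/no answer; 8.1.1 defines a reaction broadly. Protocol 8.3 requires all SAEs up to 30 days after the final dose to be reported, whatever their cause.
- **Backstops.** The QTcF and ECG criteria ignore relatedness. The investigator, the sponsor and the DRC can act on discretion under 3.3.1. SAP 3.9.1 also tabulates all TEAEs and all serious TEAEs.

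These limits stand and bound the consequence. Discretion does not make a mandatory rule consistent when its input is defined in two ways.

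**Conclusion.** The point holds as an inconsistency in a stated rule. Two of the four combinations of timing and other cause have no assigned answer. In one of them, plausible timing with another identifiable cause, the *Yes* definition contradicts both its own label and 8.1.1. No other section resolves it.

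The established reach is four of eight suspension criteria solely and a fifth in part, one of two cessation criteria, and three of eight SAP overview rows. The supportable consequence is that the same event can be classified differently by different investigators. The direction and size of any effect on triggers or tables cannot be derived, because the documents give neither event rates nor the share of events with a competing cause. The probabilities above rest on assumed values.

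The change should be made: it is cheap and bears on safety rules.

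**What to change.** Reconcile the causality text in Protocol 8.1.3 with 8.1.1 so that *Yes* and *No* are complements, consistent with the protocol's own 8.1.1 standard. *Yes* would cover any event for which causation by study drug is at least a reasonable possibility, whether or not another cause is also possible, and *No* would cover every other event. This removes the clash between the exclusion of other causes and the possible-relatedness label, and aligns the *No* label with its text.

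State in the protocol that the references to relatedness in 3.3.1 and 3.3.2 use this single definition. State in the SAP that the drug-related rows in 3.9.1, and the Per-Protocol exclusion in 3.4.3, do the same. Leave the suspension and cessation thresholds as they are.

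The cost is wording in the protocol, the SAP and the eCRF guidance. Somewhat more events may be classed as related, so DRC reviews may occur slightly more often.

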## 8.2 Serious Adverse Events

An adverse event or adverse reaction is considered serious if, in the view of either the Investigator or Sponsor, it results in any of the following outcomes:

- Death.
- A life-threatening adverse event.

Note: An adverse event or adverse reaction is considered “life-threatening” if, in view of either the Investigator or Sponsor, its occurrence places the subject at immediate risk of death. It does not include an event that, had it occurred in a more severe form, might have caused death.

- Requires hospitalization or prolongation of existing hospitalizations.

Note: Any hospital admission with at least 1 overnight stay will be considered an inpatient hospitalization. An emergency room or urgent care visit without hospital admission will not be recorded as a SAE under this criterion, nor will hospitalization for a procedure scheduled

or planned before signing of informed consent, or elective treatment of a pre-existing condition that did not worsen from Baseline. However, unexpected complications and/or prolongation of hospitalization that occur during elective surgery should be recorded as adverse events and assessed for seriousness. Admission to the hospital for social or situational reasons (ie, no place to stay, live too far away to come for hospital visits, respite care) will not be considered inpatient hospitalizations.

- A persistent or significant disability/incapacity or substantial disruption of the ability to conduct normal life functions.
- A congenital anomaly/birth defect.
- An important medical event.

Note: Important medical events that do not meet any of the above criteria may be considered an SAE when, based upon appropriate medical judgment, they may jeopardize the subject and may require medical or surgical intervention to prevent 1 of the outcomes listed above. Examples of such medical events include allergic bronchospasm requiring intensive treatment in an emergency room or at home, blood dyscrasias or convulsions that do not result in inpatient hospitalizations, or the development of drug dependency.

### 8.3 Serious Adverse Event Reporting – Procedures for Investigators

#### Initial Reports

All SAEs occurring from the time of first dose of study drug until 30 days following the final dose of study drug must be reported to [REDACTED] within 24 hours of the knowledge of the occurrence. After the 30-day reporting window, any SAE that the Investigator considers related to study drug must be reported to [REDACTED] or the Sponsor/designee. Of note, reporting of SAEs after the follow-up phone call 72 hours after discharge is dependent on spontaneous reporting by the subject. The Investigator is not required to have further contact to elicit this information after completion of the follow-up phone call but should instruct the subject to contact the site to report any such events.

To report the SAE, complete the SAE form electronically in the electronic data capture (EDC) system for the study. When the form is completed, [REDACTED] personnel will be notified electronically by the EDC system and will retrieve the form. If the event meets serious criteria and it is not possible to access the EDC system, send an e-mail to [REDACTED] at [REDACTED] or call the (b) [REDACTED] reporting line (phone number listed below), and fax/e-mail the completed paper SAE form to [REDACTED] (fax number listed below) within 24 hours of awareness. When the EDC system becomes available, the SAE information must be entered within 24 hours of the system becoming available.

Safety Contact Information: [REDACTED]

[REDACTED]  
[REDACTED]  
[REDACTED]  
[REDACTED]

#### Follow-Up Reports

The Investigator must continue to follow the subject until the SAE has subsided or until the condition becomes chronic in nature, stabilizes (in the case of persistent impairment), or the subject dies.

Within 24 hours of receipt of follow-up information, the Investigator must update the SAE form electronically in the EDC system for the study and submit any supporting documentation (eg, patient discharge summary or autopsy reports) to [REDACTED] via fax or e-mail. If it is not possible to access the EDC system, refer to the procedures outlined above for initial reporting of SAEs.

#### **8.4 Pregnancy Reporting**

If a subject becomes pregnant during the study or within the safety follow-up period defined in the protocol, the Investigator is to stop dosing with study drug(s) immediately and the subject should be withdrawn from the study. Early termination procedures should be implemented at that time.

A pregnancy is not considered to be an adverse event or SAE; however, it must be reported to [REDACTED] within 24 hours of knowledge of the event. [REDACTED] will then provide the Investigator/site the Exposure In Utero (EIU) form for completion. The Investigator/site must complete the EIU form and fax or e-mail it back to [REDACTED]

If the female partner of a male subject becomes pregnant while the subject is receiving study drug or within the safety follow-up period defined in the protocol, the Investigator should notify [REDACTED] as described above.

The pregnancy should be followed until the outcome of the pregnancy, whenever possible. Once the outcome of the pregnancy is known, the EIU form should be completed and faxed/e-mailed to [REDACTED]. If the outcome of the pregnancy meets the criteria for immediate classification as an SAE (ie, postpartum complication, spontaneous abortion, stillbirth, neonatal death, or congenital anomaly), the Investigator should follow the procedures for reporting an SAE.

#### **8.5 Expedited Reporting**

The Sponsor will report all relevant information about suspected unexpected serious adverse reactions that are fatal or life-threatening as soon as possible to the FDA and in any case no later than 7 days after knowledge by the Sponsor/designee of such a case, and the relevant follow-up information will subsequently be communicated within an additional 8 days.

All other suspected unexpected serious adverse reactions will be reported to the FDA as soon as possible but within a maximum of 15 days of first knowledge by the Sponsor/designee.

The Sponsor/designee will also inform all Investigators as required.

#### **8.6 Clinical Laboratory Evaluations**

Safety laboratory tests will include chemistry, hematology, coagulation, prolactin, and urinalysis. See [Appendix B](#) for a complete list of analytes.

Safety laboratory tests will be evaluated at the times indicated in the Schedule of Procedures table in [Appendix A](#).

Abnormal screening laboratory tests may be repeated no more than 2 times for eligibility purposes.

If, in the opinion of the Investigator, any subject has a clinically significant abnormal laboratory finding in comparison to the value at the time of randomization or unresolved TEAEs, additional follow-up visits will be scheduled. Subjects will be followed approximately once a week (or more frequently as deemed appropriate) until the Investigator determines that repeat laboratory findings are clinically unremarkable in comparison to baseline, or unresolved adverse events return to prestudy levels or clinically acceptable levels.

If a subject experiences an SAE for which follow-up laboratories and review are required, the Investigator will schedule additional postdose visits as necessary.

If, in the opinion of the Investigator, any subject has a clinically significant adverse event at the follow-up call, the Investigator will provide additional follow-up until the adverse event returns to clinically acceptable levels.

The safety laboratory sample collection times may be refined based on emerging data to ensure study objectives are met.

## **8.7 Vital Signs**

Vital signs, including heart rate, blood pressure, respiration rate, and temperature, will be measured at the times indicated in the [Schedule of Procedures table](#) in Appendix A using the following standardized procedures:

- Prior to measuring vital signs, the subject should be sitting for a minimum of 5 minutes with his/her back supported, feet flat on the floor, and his/her measurement arm supported so that the midpoint of the manometer cuff is at heart level.
- An appropriately sized cuff should be used with the bladder centered over the brachial artery.
- The cuff size and arm used for the measurement should be recorded. Whenever possible, the same arm should be used for all vital sign assessments throughout the study.
- Blood pressure should be recorded to the nearest whole number on an automatic device.

## **8.8 Electrocardiograms**

Twelve-lead ECGs will be performed at the times indicated in the Schedule of Procedures table in Appendix A.

Every effort will be made to eliminate any sources of physical (including any movement, eating, or drinking) or electrical interference. During these assessments, subjects are not permitted to use cell phones, iPods, laptop computers, tablets, or any type of battery-operated or electrical device, and all of these devices must be turned off during the assessments.

All 12-lead ECGs will be performed in triplicate approximately 1 minute apart after the subject has been resting in the supine position for at least 10 minutes. The average QTcF will be used for eligibility and safety assessments. Twelve-lead ECGs will be printed and will be interpreted as soon as possible by an Investigator (or Subinvestigator for Screening Visit only). All ECGs collected at the time of randomization and throughout the treatment period must be evaluated for the presence of abnormalities by a qualified physician. A digital recording of all ECGs for randomized subjects will be submitted to a central reviewer. The central overread ECG data will be utilized for all safety assessments and analyses.

Standard ECG parameters will be measured, and the following ECG parameters will be recorded:

- QRS interval
- Heart rate
- RR interval
- QT interval
- QTc (QTcF)

Investigators should contact the Sponsor or designee if any clinically meaningful changes from baseline are noted on review. Please refer to [Appendix C](#) for ECG alert criteria guidance.

